2.7. Devices usage in the study

2.7.1. Run-in Phase

The Guardian™ Link 3 transmitter and Guardian™ Sensor 3 will be used in a blinded manner to collect CGM data for 2 weeks at baseline in all participants. The Guardian™ Link 3 transmitter will not be linked to a MiniMed™ pump, and therefore the sensor data will not be visible to the subject.

The data will be downloaded from the transmitter in the hospital to a computer by study team members, using a transmitter dock (Dock) and a specific software (Download Utility software). This data will not be used for therapy adjustment during the study. It will only be used for study data analysis.

2.7.2. MDI/CSII Group

Blinded CGM will be used at study end for 2 weeks to collect CGM data in the MDI/CSII group. The process will be the same as described for the run-in phase.

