2.3.2. Study phase

Both groups will have a similar number of visits in order to minimize bias. However, the AHCL group will have 2 additional visits to allow for patients to be trained on the AHCL system.

MDI/CSII group:

The patient continues MDI/CSII treatment as per routine procedures

- Visit 1 (day 0, can be combined with the randomization visit): BG meter data download, data review and optimization of MDI management.
- Visit 2 (Visit 1 + 14 days, window +/- 3 days): BG meter data download, data review and optimization of MDI management
- Visit 3 (Visit 2 + 14 days, window +/- 3 days – month 1): BG meter data download, data review and optimization of MDI/CSII management
- Visit 4 (month 3): BG meter data download, data review and optimization of MDI/CSII management
- Visit 5 (month 6): BG meter data download, data review and optimization of MDI/CSII management, blinded CGM evaluation start. Preliminary evaluation
- Visit 6 (month 9) – *phone call*
- Visit 7 (month 12 minus 14 days) - *phone call*: blinded CGM - sensor change.
- Visit 8 (Visit 6 + 6 days, window +/- 1 day): QoL questionnaire, blood sample for HbA1c lab test, blinded CGM data download, . vascular status : Intima-media thickness-IMT, Flow-Mediated Dilatation -FMD and Laser Doppler Flowmetry- LDF.
-

Study conclusion.

AHCL group:

- Visit 1 (day 0, can be combined with the randomization visit): the patient will get the pre-reading materials on the 780G system, to be read before Visit 2. CGM training and initiation.
- Visit 2 (Visit 1 + 1 day, window +7 days): 780G system training and initiation in Manual Mode.
- Visit 3 (Visit 2 +3 days, window +3 days): 780G system data download. Auto Mode readiness assessment. 780G system initiation in Auto Mode with AHCL control
- Visit 4 (Visit 3 + 3 days, window +1 day) – phone call: Auto Mode initiation follow-up.
- Visit 5 (Visit 4 + 7 days, window +/- 3 days): 780G system data download, therapy assessment and optimization
- Visit 6 (Visit 5 + 14 days, window +/- 3 days, month 1): 780G system data download, therapy assessment and optimization
- Visit 7 (month 3): 780G system data download, therapy assessment and optimization
- Visit 8 (month 6): 780G system data download, therapy assessment and optimization. Preliminary evaluation of efficacy and safety (see primary and secondary endpoints except for vascular status assessment)
- Visit 9 (month 9):

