- Visit 10 (month 12): 780G system data download, QoL questionnaire, blood sample for HbA1c lab test, vascular status : Intima-media thickness-IMT, Flow-Mediated Dilatation -FMD and Laser Doppler Flowmetry- LDF.
-
-

Study Conclusion

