2.6. Study endpoints

Primary endpoint:

- Between group difference in the percentage of time spent within range with sensor glucose (SG) between 70–180 mg/dL (TIR) (3.9-10.0 mmol/L).

Secondary endpoints:

- Between groups difference in the percentage of participants achieving TIR >70%
- Between group difference in the percentage of time spent:
 - in hyperglycemic range with SG > 250 mg/dL (13.9 mmol/L)
 - in hyperglycemic range with SG > 180 mg/dL (10.0 mmol/L)
 - in hypoglycemic range with SG < 54 mg/dL (3.0 mmol/L)
 - in hypoglycemic range with SG < 70 mg/dL (3.9 mmol/L)

The above 4 endpoints will be also categorized by daytime (06:01 to 23:59) and night-time (00:00 to 06:00).

- Between group difference in the mean glucose level
- Between group difference in the glycemic variability measure by SD and CV
- Between group difference in the HbA1c levels
- Between group difference in the Diabetes Quality of Life (QoL) questionnaire score.
- Differences in baseline vs end of the study in vascular status as measured with IMT, FMD, LDF
- Difference in physical capacity indices listed in screening visit

Safety endpoints:

- Number of severe hypoglycemic episodes
- Number of DKA events
- Number of hospitalisations

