2.7.3. AHCL Group

In addition, patients from the AHCL group will use the MiniMed 780G AHCL system with Guardian™ Sensor 4.

The AHCL system will be initiated first in Manual Mode (i.e. without AHCL control) with suspend before low feature (Visit 1).

The validated protocol for SAP initiation, as previously described (8). In short, the protocol inputs the current insulin program (MDI) and calculates a 10–20% reduction in total daily dose, with a 40/60 basal/bolus distribution in four or five basal rates. Insulin-to-carbohydrate ratio (ICR) settings utilize the formula of 300–450/total daily dose (TDD) and the formula of 90–110/TDD (mmol/L) with two CF settings; the nighttime CF factor is set 10–20% higher than the daytime CF. Active insulin is set time (3 h); suspend before low feature is turned on with a threshold of 3.0–3.8 mmol/L (55–70 mg/dL), and glucose target ranges from 5.0 to 7.2 mmol/L (90–130 mg/dL).

The AHCL system will be initiated in Auto Mode (i.e. with AHCL control) at Visit 2 with the settings in the below table. The Insulin to Carb ratio (ICR) and the Active Insulin Time (AIT) may be adjusted by the physician during the study. The glucose target may not be adjusted, unless in case of safety concerns. The patients may not adjust system settings without consulting with the physician.

Basal insulin target of sensor glucose:	100 mg/dl
Insulin-Carb-Ratio:	Defined by the rule 500/TDD. TDD is the one observed during the period in Manual Mode
Active Insulin Time:	2.5 hours

At each visit, the AHCL system data will be downloaded and reviewed by the physician. The patient interaction with the system will be evaluated, included sensor calibration, bolus management (before the meals and for corrections as needed), alarms and Auto Mode exits.

At each visit, the glycemic control will be reviewed, and system settings re-assessed and adjusted as needed, including ICR, AIT and basal rates in Manual Mode.

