9. ETHICAL CONSIDERATIONS, REGULATORY APPROVAL PROCESS

INFORMATION, REGISTRATION ON CLINICALTRIALS.GOV

The study protocol and consent form will be presented for approval to the local institutional ethics committee. The study will not be started until the written approval is granted. The study will be conducted in line with the Good Clinical Practice provisions of the Declaration of Helsinki with all

amendments and local regulatory requirements. Written Patient Informed Consent (PIC) will be obtained from all participants before enrolment;

Individuals who will participate to the study will be informed that they will not be guaranteed the use of the pump either during or at the end of the study. However, those pump participants who express a preference to continue therapy and have measurable evidence of will be supported by their diabetes team in seeking the options for continuation of pump therapy.

Participants will be free to withdraw their participation to the study at any time.

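### Study-end time in range depends on still using the 780G in the AHCL arm but not in the control arm, because blinded CGM at study end is scheduled for the control arm only

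*Protocol*

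**What the plan says.** The primary endpoint in Protocol section 2.6 is the between-group difference in TIR, measured by sensor glucose. The section gives neither a time point nor a device. Section 7 compares mean TIR between the randomised arms.

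The sensor sources are set out elsewhere:

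- **Baseline, both arms (section 2.7.1).** The Guardian Link 3 transmitter and Guardian Sensor 3 "will be used in a blinded manner to collect CGM data for 2 weeks at baseline in all participants".
- **Study end, control arm (section 2.7.2).** "Blinded CGM will be used at study end for 2 weeks to collect CGM data in the MDI/CSII group". The control visit list in section 2.3.2 has a sensor change shortly before month 12, and its final visit includes "blood sample for HbA1c lab test, blinded CGM data download".
- **Study end, AHCL arm (section 2.3.2).** "Visit 10 (month 12): 780G system data download, QoL questionnaire, blood sample for HbA1c lab test", followed by the vascular measurements. No AHCL visit lists a blinded CGM start or download.
- **During the study, AHCL arm (section 2.7.3).** "In addition, patients from the AHCL group will use the MiniMed 780G AHCL system with Guardian™ Sensor 4".

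On leaving, section 9 says: "Participants will be free to withdraw their participation to the study at any time". That covers withdrawal from the study. The protocol does not say how a participant is followed who stops the device but stays in the study.

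**The concern.** Under the visit schedule, collection of the primary endpoint at study end depends on continued device use in one arm only. An AHCL participant who hands the pump back and keeps attending completes Visit 10 except for sensor glucose, because there is no 780G to download. A control participant is scheduled for blinded CGM by virtue of the allocated group.

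The people lost this way would be those who could not manage or did not accept the system, so the loss is unlikely to be random. The background section (section 1) calls adoption and acceptance by older people the open question, so this group matters to the trial's purpose. If their TIR is lower than that of continuing users, leaving them out favours AHCL on the primary endpoint, on the proportion with TIR above 70%, and probably on mean glucose and time above range. HbA1c would then rest on a fuller set of AHCL participants than TIR does.

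An analysis plan can choose an estimand or an imputation method, but it cannot recover sensor readings that the schedule never collects. The point therefore belongs in the protocol.

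**Working it through.** **Step 1. Sources of study-end TIR.**

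| Participant at study end | Scheduled sensor source | Study-end TIR |
|---|---|---|
| Control, any treatment | Blinded CGM, assigned by group (2.7.2; final control visit) | Yes |
| AHCL, on 780G in Auto Mode | 780G download (Visit 10) | Yes |
| AHCL, on 780G and sensor in Manual Mode | 780G download (Visit 10) | Yes |
| AHCL, not using 780G and sensor, still attending | None listed | No |

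The third row follows from the order of the AHCL visits. CGM starts at Visit 1 and the 780G in Manual Mode at Visit 2. Auto Mode readiness is assessed only at Visit 3, after a download.

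**Step 2. The protocol's sample size.** Inputs from section 7: means 80% and 65%, SD 15%, two-sided 5%, power 80%, attrition 15%. The standardised difference is (80 − 65)/15 = 1. A two-sample t-test needs 16.71, rounded up to 17 per arm, or 34 evaluable. Then 34/(1 − 0.15) = 40. The stated 40 reproduces and is not in question.

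**Step 3. Illustration of size.** Assumptions not in the protocol: k of the 20 AHCL participants stop the system but stay in follow-up; their TIR returns to the control mean of 65%; and they are left out of the analysis. Continuing users have the planned 80%.

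- AHCL mean over all randomised = ((20 − k) × 80 + k × 65)/20
- Overstatement if stoppers are left out = 80 minus that mean = 15k/20

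| k | AHCL mean, all randomised | Difference from 65 | Overstatement |
|---|---|---|---|
| 1 | 79.25 | 14.25 | 0.75 |
| 2 | 78.50 | 13.50 | 1.50 |
| 3 | 77.75 | 12.75 | 2.25 |

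As a share of 15 points this is 5% to 15%. If three stoppers had TIR 55% instead, the mean would be (17 × 80 + 3 × 55)/20 = 76.25, an overstatement of 3.75 points.

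For scale, the standard error of the difference with 20 per arm is 15 × √(2/20) = 4.74, so 0.75 to 2.25 points is 0.16 to 0.47 standard errors.

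**Step 4. TIR above 70%.** With a normal model, P(TIR > 70) is 0.748 at mean 80 and 0.369 at mean 65. With 3 of 20 stoppers the AHCL rate over all randomised is 0.85 × 0.748 + 0.15 × 0.369 = 0.691, against 0.748 among continuing users.

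**The case against.** **The group may be small or empty.** The protocol gives no rate of stopping the device while staying in follow-up. Its 15% is an attrition allowance, and people who leave the study would mostly have no month-12 CGM under any schedule. This stands, and it is why the figures above are only illustrative.

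**A reader might infer that anyone who does not pass the Auto Mode readiness assessment also loses TIR.** The visit order does not support this. Such a participant is already on the pump and sensor and can still yield a download in Manual Mode.

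**A reader might infer that the plan excludes stoppers and will report 80%.** No section says so. Analysis sets may be defined in an analysis plan that is not shown, and section 4 says that reasons for missing data will inform its handling. Someone who stops after month 6 also has earlier downloads that could be used. These are choices about how to fill a gap, however; they do not supply study-end readings.

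**Month 12 is not stated as the primary time point.** This is correct. It is inferred from the study-end CGM in section 2.7.2 and the content of AHCL Visit 10.

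**The visit lists are incomplete, so absence from them proves little.** AHCL Visit 9 has no content. The control schedule has its own conflict: Visit 8 is timed from Visit 6, which is month 9, and the only listed CGM start is at month 6. The opening words of section 2.7.3 could also be read as adding the 780G to blinded CGM. But section 2.7.2 names only the MDI/CSII group for study-end blinded CGM, and no AHCL visit schedules it.

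**Inclusion requires willingness to wear the system continuously.** That is a condition at entry and gives no rule for collecting data after the device is stopped.

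**Conclusion.** The concern holds in a limited form. As scheduled, an AHCL participant who is not using the 780G and its sensor at study end, but remains in follow-up, has no source of study-end TIR. Control participants are measured by group with no stated condition on treatment. That control measurement continues whatever the treatment is a reading of the protocol's silence, as no such condition is written.

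The direction probably favours AHCL for TIR. The documents give no figure that fixes the direction for hypoglycaemia, SD or CV. The size is unknown. With 20 per arm, stoppers at 65% and stoppers left out, 1 to 3 of them would overstate the planned 15-point difference by 0.75 to 2.25 points. This is modest beside the planned effect, and neither the stopping rate nor TIR after stopping comes from the protocol. The sample size of 40 is unaffected as a calculation.

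The change is worth making because it is cheap and because the missing readings cannot be recovered later.

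**What to change.** In sections 2.7.2 and 2.7.3 and at AHCL Visit 10, state that:

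1. any AHCL participant who is not wearing the 780G sensor at study end and remains in follow-up wears the same 2-week blinded Guardian CGM as the control arm before Visit 10;
2. stopping the 780G is not by itself withdrawal from the study;
3. these data count in the AHCL arm, as randomised.

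This changes measurement only, not treatment.

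**Cost.** It needs protocol wording and a two-week sensor wear for a few participants. The equipment is already used at baseline in both arms, and section 2.8.1 already provides staff training on professional CGM. The estimated effect may be slightly smaller. The blinded process uses Guardian Sensor 3 while the 780G uses Guardian Sensor 4, so the AHCL arm would contain readings from two sensor models, split by device use. The analysis should note this.

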2.7.3. AHCL Group

In addition, patients from the AHCL group will use the MiniMed 780G AHCL system with Guardian™ Sensor 4.

The AHCL system will be initiated first in Manual Mode (i.e. without AHCL control) with suspend before low feature (Visit 1).

The validated protocol for SAP initiation, as previously described (8). In short, the protocol inputs the current insulin program (MDI) and calculates a 10–20% reduction in total daily dose, with a 40/60 basal/bolus distribution in four or five basal rates. Insulin-to-carbohydrate ratio (ICR) settings utilize the formula of 300–450/total daily dose (TDD) and the formula of 90–110/TDD (mmol/L) with two CF settings; the nighttime CF factor is set 10–20% higher than the daytime CF. Active insulin is set time (3 h); suspend before low feature is turned on with a threshold of 3.0–3.8 mmol/L (55–70 mg/dL), and glucose target ranges from 5.0 to 7.2 mmol/L (90–130 mg/dL).

The AHCL system will be initiated in Auto Mode (i.e. with AHCL control) at Visit 2 with the settings in the below table. The Insulin to Carb ratio (ICR) and the Active Insulin Time (AIT) may be adjusted by the physician during the study. The glucose target may not be adjusted, unless in case of safety concerns. The patients may not adjust system settings without consulting with the physician.

Basal insulin target of sensor glucose:	100 mg/dl
Insulin-Carb-Ratio:	Defined by the rule 500/TDD. TDD is the one observed during the period in Manual Mode
Active Insulin Time:	2.5 hours

At each visit, the AHCL system data will be downloaded and reviewed by the physician. The patient interaction with the system will be evaluated, included sensor calibration, bolus management (before the meals and for corrections as needed), alarms and Auto Mode exits.

At each visit, the glycemic control will be reviewed, and system settings re-assessed and adjusted as needed, including ICR, AIT and basal rates in Manual Mode.

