7. STATISTICS CONSIDERATIONS: SAMPLE SIZE CALCULATION AND STATISTICAL ANALYSIS

Statistical Hypothesis

The null-hypothesis $H_0: TIR_{MD/CSII} = TIR_{AHCL}$ will be tested against the alternative hypothesis $H_A: TIR_{MD/CSII} \neq TIR_{AHCL}$, where $TIR_{MD/CSII}$ and TIR_{AHCL} are the mean Time in Range (70–180 mg/dL) in the MDI/CSII and the AHCL groups, respectively.

Sample size

Using data from the study previously performed at our center a mean TIR=80% (Std=15%) in the AHCL group and a mean TIR= 65% (Std=15%) in the MDI/CSII group. For a two sided two-sample t-test, a total sample size of 40 subjects is required to test the hypothesized difference in population means of 15% with a 95% confidence level, 80% power and attrition rate of 15%.

Analysis of primary endpoint

The primary analysis will use a two-sample t-test to compare the mean TIR between the randomized arms of the study. The analysis will be adjust by baseline TIR. The mean TIR in the patients in the AHCL arm will be claimed to be smaller than then mean TIR in the MDI arm if the average TIR is smaller in the AHCL arm and the associated p-value of the test is less than 0.05. No extra adjustments are needed for this nested test.

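### Does measuring follow-up TIR with a different glucose sensor in each arm call for a change to the plan?

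*Protocol*

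**What the plan says.** The primary endpoint in Protocol section 2.6 is the between-group difference in the percentage of time with sensor glucose between 70 and 180 mg/dL, so the outcome is itself a sensor reading. The devices are set out in section 2.7:

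- Run-in (2.7.1): Guardian "Sensor 3 will be used in a blinded manner to collect CGM data for 2 weeks at baseline in all participants".
- MDI/CSII arm (2.7.2): "Blinded CGM will be used at study end for 2 weeks to collect CGM data in the MDI/CSII group", and "The process will be the same as described for the run-in phase". That means Sensor 3 again.
- AHCL arm (2.7.3): "patients from the AHCL group will use the MiniMed 780G AHCL system with Guardian™ Sensor 4".

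The AHCL visit list in section 2.3.2 shows 780G downloads and no blinded CGM. Its last entry begins "Visit 10 (month 12): 780G system data download, QoL questionnaire, blood sample for HbA1c lab test". The control arm's last visit lists a blinded CGM download.

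On the analysis, section 7 says "The analysis will be adjust by baseline TIR". The sample size there assumes "a mean TIR=80% (Std=15%) in the AHCL group" against 65% with the same SD under MDI/CSII. Section 2.6 also lists "Between group difference in the HbA1c levels" as a secondary endpoint.

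**The concern.** Taken together, these sections make sensor model coincide with treatment arm at follow-up, for TIR and for every CGM-based secondary endpoint. If Sensor 4 reads systematically higher or lower than Sensor 3, the difference appears only in the AHCL arm and only after randomisation. Randomisation cannot balance it. The baseline covariate cannot absorb it either, because that covariate was recorded with Sensor 3 in both arms and carries no information about Sensor 4. Any offset would be credited to, or taken from, the AHCL system. At stake are the size of the primary estimate and, if the true effect is smaller than planned, its significance.

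**Working it through.** **Inputs from Protocol section 7.** Difference 80 − 65 = 15 points, SD 15 per arm, two-sided 5% test, 80% power, 15% attrition, total 40. Allocation is 1:1 (section 4).

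**Reproducing the plan's figure.** The two-sample t-test needs 16.7 per arm, so 17, or 34 in total. Then 34 / 0.85 = 40. The stated sample size is correct and is not in question.

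**Does the adjustment remove an offset?** Write follow-up TIR as a + r × (baseline) + (effect + b) × arm, where b is the Sensor 4 minus Sensor 3 offset in TIR points. Effect and b multiply the same arm indicator, so only their sum can be estimated. Simulated baseline-adjusted trials (17 per arm, no true effect, assumed r = 0.5) agree: b = 2, 3 and 5 gave mean adjusted differences of 2.2, 3.0 and 5.0. The offset passes through in full.

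**How large must b be to overturn the planned result?** SE = 15 × √(1 − r²) × √(2/17), with 31 degrees of freedom and t = 2.04. The protocol gives no r, so a range is assumed.

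| Assumed r | SE | Critical difference | Offset that overturns an observed 15 | Offset that overturns an observed 12 |
|---|---|---|---|---|
| 0.3 | 4.91 | 10.01 | 4.99 | 1.99 |
| 0.5 | 4.46 | 9.09 | 5.91 | 2.91 |
| 0.7 | 3.67 | 7.49 | 7.51 | 4.51 |

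Each of the last two columns is the observed difference minus the critical difference.

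**What might b be?** The protocol does not say. As an assumption, take lognormal glucose with CV 30% to 36% and a proportional sensor difference, so that TIR = P(70 < glucose < 180). Only a sensor that reads low, and so inflates AHCL TIR, can manufacture significance. Solve for the mean that gives a Sensor 4 reading of 80% (145.3 mg/dL at CV 30%, 134.1 at CV 36%), then divide glucose by 0.97 or 0.95 to undo the low reading. TIR falls by 1.4 to 2.7 points for a 3% difference and by 2.5 to 4.7 for 5%. All of these are below the smallest overturning offset, 4.99.

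At an observed 12 points (AHCL reading 77%), the same steps give 2.0 to 3.0 points for 3% and 3.4 to 5.3 for 5%, which does reach the overturning values of 2.0 to 4.5.

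**Other consequences of an assumed offset.** With no true effect and b = 3, the test rejects in 9.1%, 10.0% and 12.4% of trials (r = 0.3, 0.5, 0.7) instead of 5%. With a true 15 points and 2 points lost to the sensor, power falls from 84%, 90% and 98% to 73%, 81% and 93%.

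**The case for a change.** The strongest case for acting is that this is a design choice fixed in the protocol, and no later analysis plan can undo it. The adjustment in section 7 might give false reassurance. Stating beforehand which recording supplies AHCL TIR, over which period, and at what offset the conclusion would change costs only wording, and prevents a choice made after the data are seen.

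Much of this stands. The confounding of sensor with arm is the natural reading, and full pass-through of any offset is certain algebra. A result near 12 points would be fragile.

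Three things weigh against a change. First, the AHCL source is inferred: no section states which recording is used, and the opening of section 2.7.3 could be taken to mean that the 780G comes on top of blinded CGM. That is the weaker reading, since section 2.7.2 names only the control arm, but the gap is one that an analysis plan ordinarily fills. Second, nothing in the protocol makes a 3% to 5% sensor difference more likely than none, and the 12-point scenario is not the protocol's. Any result close to the critical difference is fragile to any small disturbance. Third, a tipping-point analysis describes the offset without reducing it. The estimate and the test would be the same with or without it.

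**Conclusion.** No change to the plan follows. The different sensors are a limitation to acknowledge when TIR is reported, not a demonstrated bias. Sensor 4 belongs to the 780G system as the protocol specifies it, and using that system's own readings while sparing AHCL participants a second device is a fair trade-off. Only same-sensor wear in both arms would remove an offset, and that is an added procedure.

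At the planned 15-point difference, the conclusion holds unless 5.0 to 7.5 points are due to the sensor. This rests on 17 completers per arm, SD 15 and an assumed correlation of 0.3 to 0.7. An assumed 5% reading difference stays below that range. The margin is thin at its edge (4.7 against 5.0, with CV 30% and correlation 0.3) and disappears at smaller observed effects, so the size of the TIR difference should be read beside the laboratory HbA1c difference. HbA1c is collected in both arms at the final visit. It does not correct TIR, but it gives an independent check on direction.

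The timing of blinded CGM differs between sections 2.3.1 (12 days), 2.3.2 (a start at month 6 in the control arm) and 2.7 (2 weeks, at baseline and study end). Those statements must be reconciled in any case before a common window can be defined. That is a separate matter, and the conclusion here does not depend on it.
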